1. LIST OF ABBREVIATIONS

AE	adverse event
ARR	annualized relapse rate
CBC	complete blood count
CI	confidence interval
cNEDA	clinical no evidence of disease activity
CRO	contract research organization
eCRF	electronic case report form
EDC	electronic data capture
EDSS	Expanded Disability Status Scale
EQ-5D-3L	EuroQoL EQ-5D, 3-level
ER	emergency room
EU	European Union
FLS	flu-like symptoms
GCP	Good Clinical Practices
GVP	Good Pharmacovigilance Practices
HIPAA	Health Insurance Portability and Accountability Act
HRQoL	health-related quality of life
ICF	informed consent form
ICH	International Conference on Harmonisation
IEC	Independent Ethics Committee
IFN	interferon
IFN β	interferon beta
IFN β -1a	interferon beta-1a
IL	interleukin
IRB	Institutional Review Board
ISR	injection site reaction
MedDRA	Medical Dictionary for Regulatory Authorities
MRI	magnetic resonance imaging
MS	multiple sclerosis
PHI	protected health information
POP	Plegridy Real World Effectiveness and Safety Observational Program
Prescribing Physician	The Prescribing Physician is also the Principal Investigator

CONFIDENTIAL

The information contained herein may not be used, disclosed, or published without the written consent of Biogen MA Inc.

PRO	patient-reported outcome
RMS	relapsing multiple sclerosis
SAE	serious adverse event
SAP	statistical analysis plan
SC	subcutaneous
SD	standard deviation
STROBE	STrengthening the Reporting of OBservational studies in Epidemiology
US	United States
VAS	visual analog scale

CONFIDENTIAL

The information contained herein may not be used, disclosed, or published without the written consent of
Biogen MA Inc.

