	
for specific time intervals (e.g., from Year 1 to Year 2, etc.) along with 95% CIs for the proportions.
 
Annualized relapse rate (ARR) will be analyzed using a negative binomial model, adjusted for appropriate prognostic factors, and time-to-sustained disease progression for at least six months will be analyzed using Kaplan-Meier estimates. In addition, Poisson regression models and Cox proportional hazard models might be applied to assess the association between ARR/time to sustained disability progression and certain demographic variables, baseline disease characteristics, or medical history variables of interest, respectively.
 
All SAEs will be summarized by listing all standard terms of SAEs occurring during the study with counts and percentages. All AEs including FLS and ISRs will be summarized by listing all standard terms of AEs occurring during the study, along with counts and percentages. FLS scores will also be summarized using mean, standard deviation (SD), median, and maximum and minimum values.
 
Longitudinal evaluation of PROs using a linear regression model may be performed to evaluate patients' long term experience (e.g., change over time).

Milestones:	
Start of data collection: 03 December 2014
 
End of data collection: Q1 2022 (estimated)
 
Study progress reports: Not applicable*
 
Interim reports: Not applicable*
 
Final report of study results: Within 12 months of last data collection (estimated to be June 2022)
 
* No commitment by Biogen to provide study progress reports or interim progress reports to regulators is currently in place.

CONFIDENTIAL

The information contained herein may not be used, disclosed, or published without the written consent of Biogen MA Inc.

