8.1.2. Secondary Endpoints

Secondary endpoints will address non-serious AEs of special interest and other clinical effectiveness and non-safety related objectives as follows:

- Plegridy prescription and utilization patterns will be evaluated by assessment of prescribed dosing frequency, duration of Plegridy use, and primary reason for discontinuation of Plegridy (see Section 8.3.3 “MS Treatments and Concomitant Medications”).
- Effectiveness of Plegridy on specific MS clinical disease activity will be evaluated by assessment of relapse-related endpoints (e.g., ARR, time-to-first relapse, proportion of patients with relapse, and distribution of number of relapses and disability progression-related endpoints based on the EDSS (e.g., proportion of patients with progression and time-to-sustained progression for at least six months).

CONFIDENTIAL

The information contained herein may not be used, disclosed, or published without the written consent of Biogen MA Inc.

- Safety and tolerability of Plegridy will be assessed by the incidence proportion and incidence rates of non-serious AEs, including but not limited to FLS, ISRs, and AEs (including laboratory abnormalities) leading to treatment discontinuation.
- The impact of the severity of FLS on the ability to successfully manage symptoms via prophylaxis will be evaluated using the patient-reported FLS-VAS.
- Changes in FLS assessment and FLS-VAS over time.
- Changes in HRQoL measures will be evaluated over time using the EQ-5D-3L.
- Healthcare resource consumption will be evaluated by assessment of endpoints such as MS-related and non-MS-related physician visits, specialists' visits, use of physiotherapy, hospitalizations and lengths of stay, and emergency room (ER)/department visits.
- Patient-reported treatment adherence to Plegridy will be assessed using the Treatment Adherence Questionnaire for all patients.

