8.6.5.4. Secondary Endpoints Analysis

Plegridy prescription and utilization

Duration of Plegridy use and prescribed dosing frequency will be summarized both descriptively and categorically, as appropriate. Primary reasons for discontinuation of Plegridy will be tabulated. Plegridy use will also be described by concomitant medications.

Clinical disease activity (relapse activity and disability progression)

Relapse activity will be assessed by evaluating by relapse-related endpoints. These analyses will include the following parameters:

- ARR: defined as the total number of relapses divided by the number of patient-years on study divided by 12 months.
- Time to first relapse: defined as time (in days) between the date of initiating Plegridy to date of onset of first relapse following Plegridy initiation. Please refer to Section 8.3.6 for the definition of relapse.

CONFIDENTIAL

The information contained herein may not be used, disclosed, or published without the written consent of Biogen MA Inc.

- Proportion of patients with relapse: The proportion of patients with relapse will be described by counts and percent.
- Distribution of the number of relapses: The distribution of the number of relapses will be summarized using mean (SD) and median (minimum and maximum).

Disability progression will be assessed by evaluating disability progression-related endpoints. These analyses will include the following parameters:

- Proportion of patients with sustained progression for at least six months. For the purposes of this study, progression is defined as at least a 1.0 point increase from baseline in EDSS ≥ 1.0 or at least a 1.5 point increase from a baseline EDSS = 0.
- Time to sustained progression for at least six months.

ARR will be analyzed using a negative binomial model, adjusted for appropriate prognostic factors. If the data are under-dispersed or if the negative binomial regression model does not converge, a Poisson regression model with the same covariates will be used instead. Time to sustained progression will be analyzed using Kaplan-Meier estimates.

In addition, Poisson regression model and Cox proportional hazard model might be applied to assess the association between certain demographic variables, baseline disease characteristics, or medical history variables of interest and ARR/time to sustained disability progression, respectively.

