8.6.7. Sample Size Considerations

While no formal statistical hypotheses are being tested in this descriptive observational study, 1100 patients newly or currently prescribed with Plegridy are being targeted for enrollment. All patients will be followed for up to five years, and follow-up is planned regardless of whether patients discontinue treatment with Plegridy. Because this is a long-term observational program, a sample size of 1100 patients was chosen to ensure a reasonable likelihood of observing rare AE events over a 5-year period and to provide informative CIs for SAE incidence and incidence rate point estimates. Based on the withdrawal/discontinuation rates observed in the Plegridy Phase III clinical trial (Study

CONFIDENTIAL

The information contained herein may not be used, disclosed, or published without the written consent of Biogen MA Inc.

105MS301, 1-year) and prior Biogen observational studies, it is expected that approximately 3520–3960 person-years of follow-up will accrue.

With a sample size of 1100 patients, the probability of observing an event with an incidence rate of 0.10% (1/1000 persons) will be approximately 67%; the probability of observing an event with an incidence rate of 0.09% (90/100,000 persons, or 1/1111 persons) will be approximately 63%; the probability of observing an event with an incidence rate of 0.08% (80/100,000 persons, or 1/1250 persons) will be approximately 59%; and the probability of observing an event with an incidence rate of 0.054% (54/100,000 persons, or 1/1851 persons) will be approximately 48%.

For the co-primary endpoint of cNEDA, assuming a dropout rate up to 20%, a sample size of 1100 patients, and an expected 68.4% of patients free from clinical disease activity at the end of one year (Study 105MS301, 1-year), a two-sided 95% CI for the observed proportion of patients free from measured clinical disease activity at the end of one year using large sample normal approximation will extend 0.027 to 0.031 from the observed proportion for an expected proportion of 0.684.

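### The ARR formula in Protocol Section 8.6.5.4 adds a division by 12 months to a denominator already in patient-years; taken literally, the descriptive rate is 12 times too low or 12 times too high

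*Protocol*

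**What the plan says.** Protocol Section 8.6.5.4, under clinical disease activity, defines the endpoint in one sentence: "ARR: defined as the total number of relapses divided by the number of patient-years on study divided by 12 months". The list of abbreviations in Section 1 expands ARR as "annualized relapse rate". Section 8.1.2 places it among the secondary endpoints, within the "relapse-related endpoints (e.g., ARR, time-to-first relapse, proportion of patients with relapse" group.

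On the analysis, Section 8.6.5.4 adds only that "ARR will be analyzed using a negative binomial model, adjusted for appropriate prognostic factors", with Poisson regression as the fallback. The Abstract says the same about the negative binomial model and gives no formula. Neither place states an offset or its time unit. Section 8.6.7 expresses expected follow-up in years: "3520–3960 person-years of follow-up will accrue". No other part of the protocol gives a different ARR formula or corrects this one.

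**The concern.** An annualized rate needs exactly one conversion to years. If follow-up is counted in patient-years, that conversion has already been made. If it is counted in patient-months, the months must be divided by 12. The sentence does both. It also has no brackets, so it does not show whether the 12 divides the rate or the denominator.

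At stake is the descriptive ARR. Section 8.6.6 plans annual interim analyses, to be submitted at least as congress abstracts, so a figure programmed from this sentence could be made public before the final report. This is not a detail left to the SAP: the protocol chose to fix the formula, and the formula it fixed does not give the quantity it names.

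**Working it through.** The protocol states no ARR value, relapse count or ARR-based sample size, so there is no figure of its own to reproduce. The check is of the formula.

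**Inputs**
- PY, patient-years on study: 3,520 to 3,960 (Section 8.6.7). These equal 1,100 × 3.2 and 1,100 × 3.6 years, so follow-up is already in years.
- R, total relapses: not given. R = 1,000 is assumed for the example, and true ARRs of 0.1 to 0.4 are assumed for the range.

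**Formulas**
- Annualized rate: R / PY
- Reading A, left to right: (R / PY) / 12, a rate per patient-month
- Reading B, denominator first: R / (PY / 12), relapses per 12 patient-years
- Probable intention: R / (patient-months / 12) = R / PY

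**Example with R = 1,000 and PY = 3,520**
- Annualized rate: 1,000 / 3,520 = 0.284
- Reading A: 0.284 / 12 = 0.024
- Reading B: 1,000 / (3,520 / 12) = 1,000 / 293.3 = 3.41

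**Over a range of assumed true ARRs**

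| True ARR | Reading A | Reading B | R / (patient-months / 12) |
|---|---|---|---|
| 0.1 | 0.0083 | 1.2 | 0.1 |
| 0.2 | 0.0167 | 2.4 | 0.2 |
| 0.3 | 0.025 | 3.6 | 0.3 |
| 0.4 | 0.0333 | 4.8 | 0.4 |

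The table is the same at 3,520 and at 3,960 patient-years. The factor is exactly 12 whatever R and PY are; only its direction depends on the reading.

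**The case against.** The strongest reply is that this is a drafting slip, probably for patient-months divided by 12, which a competent programmer would put right. The endpoint's name says what is meant, Section 8.6.5.2 leaves full analysis detail to a SAP that was not available for this review, and a twelvefold error in a familiar rate would stand out in the output. There is also a third reading, in which 12 months simply means one year. It leaves the number unchanged, but it makes the second division pointless and is strained. All of this bears on how likely harm is. It does not make the sentence correct.

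Three stronger readings are tempting, and the document does not support them:
- A reader might infer that the reported ARR will be wrong twelvefold. That follows only if the sentence is programmed as written.
- A reader might infer that the descriptive ARR must disagree with the negative binomial result. The protocol does not state the model's offset or time unit, so this cannot be shown. If the model did use log person-years, its rate would not carry the error.
- A reader might take ARR as the leading relapse endpoint, and the comparison with the pivotal trial as compromised. ARR is listed first among the relapse endpoints, but no ranking is stated. Section 6.2.2 reports the pivotal trial only as relative ARR reductions (36% and 28%), which a constant factor would not change.

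**Conclusion.** The definition is wrong as written. Both arithmetic readings miss an annualized rate by exactly a factor of 12, in opposite directions, and nothing elsewhere in the protocol resolves which was meant. That part needs no assumption; the 0.284, 0.024 and 3.41 rest on the assumed 1,000 relapses.

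The reach is limited. ARR is a secondary endpoint in a descriptive study without formal hypothesis tests. SAE incidence and cNEDA, the co-primary endpoints of Section 8.1.1, do not use the formula, and neither do the sample-size statements of Section 8.6.7. Rate ratios are unaffected because a constant factor cancels. The exposure is confined to the absolute descriptive ARR, and only if the sentence is followed literally.

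**What to change.** Delete the division by 12 months at the end of the definition, so that it reads: ARR = total number of relapses / total patient-years on study. Equivalently, write: total number of relapses divided by (patient-months on study / 12), keeping the brackets. Keep the existing on-study denominator. Changing the definition of the time counted, or specifying a model offset, is not needed to correct this error.

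Check that any ARR definition in the SAP and in the interim or final table specifications matches. The cost is one phrase in the protocol and that check; data collection and study conduct do not change.

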8.2. Setting

8.2.1. Inclusion Criteria

To be eligible to participate in this study, patients must meet the following eligibility criteria at the time of enrollment:

1. Patient and or legal representative is willing and able to understand the purpose and risks of the study and provide signed and dated informed consent and authorization to use protected health information (PHI) in accordance with national and local patient privacy regulations.
2. Patient with MS who is newly, or is currently, prescribed Plegridy according to local label including patients who participated in Study 105MS302 or Study 105MS303.
3. Patient age 18 years or older.
4. Patient willing and able to complete PROs with minimal assistance.

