Eligible patients may be naïve to Plegridy at the time of enrollment, but need not be naïve to other MS treatments, and must not currently be enrolled in any other clinical trial of an investigational product, unless according to the study Medical Director it does not conflict with the observational study (e.g., health economic studies). Patients with previous exposure to Plegridy will be evaluated separately from patients who are newly prescribed Plegridy because prevalent Plegridy-users may be more or less likely to experience AEs, may fail to report AEs that occurred before study enrollment, or may have discontinued Plegridy treatment due to an AE. Patients participating in other clinical studies are excluded so as not to unduly confound causality assessments when the safety profile of a concomitant experiment agent has yet to be established and/or the physician is blinded to the patient's treatment assignment.

The decision to enroll a patient in this study must not be made until after the Prescribing Physician and patient decide to begin Plegridy treatment and Plegridy treatment has been prescribed. Patients (or their legally authorized representative) agreeing to participate in the study will read and sign the informed consent and confidentiality statements. Enrollment data will be collected by the Prescribing Physician at the routine clinical visit at which Plegridy is first prescribed. For patients with previous exposure to Plegridy prior to enrollment, data will be collected from the time of first dose of Plegridy through enrollment in this or previous studies (see Section 8.3.1 for details). During enrollment, the Prescribing Physician will also inform female patients of childbearing potential if a pregnancy registry is being conducted independently of this observational study.

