8.3.2. Demographics, Baseline Disease Characteristics, and Treatment History

The following data will be collected at baseline for all enrolled patients:

- Documentation of signed informed consent.
- Demographic: age at enrollment (years), sex, race (where allowed by local regulation).
- Relevant medical history and co-morbidities: assessment of clinically significant medical and surgical history and concomitant diseases, and known cardiovascular risk factors (e.g., smoking, alcohol consumption, patient and family history of high cholesterol, high blood pressure, cardiac disease, peripheral artery disease, arrhythmia, cerebrovascular disease, and diabetes mellitus).
- MS disease history (type of MS, relapse history, and the latest EDSS score based on last neurologic examination conducted prior to enrollment) and the results of the latest brain MRI scan, which may include lesion count (if available).
- Prior use and duration of therapies for MS (if any; e.g., start and stop dates, initial dose, dose reductions or escalations, prescribed dosing frequency, reason for discontinuation).
- Prior use and duration of immunomodulatory, immunosuppressive (including corticosteroids), and anti-neoplastic agents (if any; e.g., start and stop dates, initial dose, dose reductions or escalations, prescribed dosing frequency, reason for discontinuation).
- Prior use and duration of all other concomitant medications (e.g., start and stop dates, initial dose, dose reductions or escalations, prescribed dosing frequency, reason for discontinuation).
- History of FLS on previous IFN therapy (e.g., history of chills, body aches, pyrexia, myalgia, or muscle aches).
- Ambulation status at time of initiating Plegridy.
- MRI results (e.g., lesion counts), if available.
- CBC with differential, if consistent with routine clinical practice and local regulations.
- Other laboratory tests recommended in local label (e.g., liver and renal function tests, urinalysis) if consistent with routine clinical practice and local regulations.
- Concomitant use (i.e., at enrollment) of immunomodulatory, immunosuppressive (including corticosteroids), and anti-neoplastic agents, and other approved MS therapies (if any).
- Concomitant use (i.e., at enrollment) of non-MS therapy medications (if any).

CONFIDENTIAL

The information contained herein may not be used, disclosed, or published without the written consent of Biogen MA Inc.

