EDSS information (Functional System Scores and Ambulation Scores), based on neurological examination, if consistent with local practice	X	X	X	X
Neurological assessment, if not EDSS	X	X	X	X
MS relapse information, if applicable	X	X	X	X
Use of immunomodulatory, immunosuppressive (including corticosteroids), and anti-neoplastic agents, and other approved MS therapies after discontinuing Plegridy, if applicable		X	X	X
Pregnancy status and nursing status (female patients)	X	X	X	X
PROs ⁴ : EQ-5D-3L, FLS, healthcare resource consumption questionnaire, treatment adherence questionnaire, ⁵ FLS-VAS ⁶	X ⁴	X	X	X
AEs of special interest (FLS, ISR)	X ----->			
AEs [including laboratory abnormalities] leading to treatment discontinuation)	X ----->			
SAEs	X ----->			

CONFIDENTIAL

The information contained herein may not be used, disclosed, or published without the written consent of Biogen MA Inc.

1. Data are to be collected according to local clinical practice, preferably within four weeks (before or after) the time of a clinic visit. Data collection will be inclusive of healthcare visits (e.g., clinic, emergency room, etc.) resulting in a diagnosis of MS relapse that occurs within the three-month (Year 1) or six-month (Year 2 through Year 5) data collection period. MS relapse will be confirmed by the Prescribing Physician (see Section 8.3.6 for the relapse definition). No visits or examinations, laboratory tests or procedures are mandated as part of this study.
2. Baseline is defined as the date of enrollment. Data will be collected from the time of first dose through enrollment for patients who had exposure to Plegridy prior to study enrollment.
3. If a patient withdraws prior to completing the study, all information already collected as part of the study will be retained for the analysis; however, no further efforts will be made to obtain or record additional information regarding the patient.
4. PROs may be completed electronically or on paper at a routine visit if consistent with local regulations. If a patient does not complete his/her PROs during the clinic visit then he/she can complete the PROs electronically via the secure, personalized link within four weeks of his/her routine clinical visit. PROs completed on paper will be entered into the EDC by the site.

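### Time to first relapse is clocked from Plegridy initiation even for patients already on Plegridy at enrollment, which overstates relapse-free time in that group if relapse prompts stopping or earlier relapses are missed

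*Protocol*

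**What the plan says.** - **Origin.** Section 8.6.5.4 lists time to first relapse among the secondary relapse endpoints, "defined as time (in days) between the date of initiating Plegridy to date of onset of first relapse following Plegridy initiation". It has no separate rule for patients who started Plegridy before the study.
- **Eligibility.** Section 8.2.1 admits a "Patient with MS who is newly, or is currently, prescribed Plegridy according to local label", including patients from Studies 105MS302 and 105MS303.
- **Baseline.** Footnote 2 to Table 4 (Section 16.1) says: "Baseline is defined as the date of enrollment".
- **Retrospective data.** The same footnote continues: "Data will be collected from the time of first dose through enrollment for patients who had exposure to Plegridy prior to study enrollment". Section 8.2.4.1 repeats the provision, and Section 8.3.2 collects "MS disease history (type of MS, relapse history, and the latest EDSS score" at baseline. Sections 9.2 and 9.4 provide for linkage to the data of 105MS302 and 105MS303.
- **Cohorts.** Sections 8.2.4.1 and 8.6.3 have naive and experienced patients analysed separately. The reason given in Section 8.2.4.1 is that "prevalent Plegridy-users may be more or less likely to experience AEs, may fail to report AEs that occurred before study enrollment"; stopping the drug because of such an event is named there as a further possibility.
- **Companion endpoints.** In Section 8.6.5.4 the annualized relapse rate (ARR) uses person-time in the study. In Section 8.6.5.3 clinical no evidence of disease activity (cNEDA) runs from baseline.

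**The concern.** For an experienced patient the clock starts before study entry, and entry depends on Plegridy still being prescribed. A patient who relapsed and stopped between initiation and the chance to enroll cannot be in the cohort, while a comparable patient who did not relapse can. Treating the whole period since initiation as ordinary time at risk gives the enrolled patients credit for time they had to get through on treatment. The protocol recognises this kind of selection for adverse events but does not carry it over to relapse. Separate cohort analysis protects the naive result; it does not correct the origin within the experienced group.

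The experienced cohort's relapse-free time could therefore look too favourable. It would also sit beside an ARR and a cNEDA proportion that run on a different clock in the same patients. Long-term effectiveness is a stated objective, and Section 8.6.6 sends interim data to congresses.

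**Working it through.** The protocol gives no figure for this endpoint, so there is nothing to reproduce. The check asks how far the stated origin can move the 1-year relapse-free proportion among experienced patients.

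**Inputs from the protocol.** Follow-up lasts up to five years after enrollment, so no one is administratively censored before one year from initiation. Section 8.6.7 expects 68.4% with cNEDA at one year. At a constant hazard, that caps the relapse hazard at −ln(0.684) = 0.38 per year.

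**Assumptions not in the documents.** Relapse hazard λ; prior exposure a uniform on 0 to A years; probability q that a patient stops Plegridy at first relapse; background stopping μ = 0.10 per year, unrelated to relapse.

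**Formula, all pre-enrollment relapses captured.** A patient with prior exposure a is enrollable with probability e^(−μa)·[1 − q(1 − e^(−λa))]. With S(1) = e^(−λ), the observed 1-year proportion is

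[S(1)·I − q·N] / [I − q·D], where

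- I = ∫₀ᴬ e^(−μa) da
- D = ∫₀ᴬ e^(−μa)(1 − e^(−λa)) da
- N = ∫₁ᴬ e^(−μa)(e^(−λ) − e^(−λa)) da (zero if A ≤ 1)

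**Numbers for λ = 0.25, A = 2.**

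- S(1) = 0.7788
- I = (1 − e^(−0.2))/0.1 = 1.8127
- D = 1.8127 − (1 − e^(−0.7))/0.35 = 1.8127 − 1.4383 = 0.3744
- N = 0.7788 × 0.8611 − 0.5946 = 0.0760
- S(1)·I = 1.4117

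| q | Calculation | Observed | Shift from true 0.779 |
|---|---|---|---|
| 0 | 1.4117 / 1.8127 | 0.779 | 0 |
| 0.2 | 1.3965 / 1.7378 | 0.804 | +2.5 points |
| 0.5 | 1.3737 / 1.6255 | 0.845 | +6.6 points |
| 0.6 | 1.3661 / 1.5881 | 0.860 | +8.1 points |

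**Range.** For λ of 0.15, 0.25 and 0.38, A of 1, 2 and 4 years, and q from 0.2 to 0.6, the same formula gives shifts from +1.2 points (λ = 0.15, A = 1, q = 0.2) to +10.6 points (λ = 0.38, A = 2, q = 0.6). Most lie between 2 and 10.

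**Second model.** Here the hazard is gamma-distributed with mean 0.3 per year (shape 2, scale 0.15), prior exposure is 0–3 years and there is no background stopping. The true value is 1.15^(−2) = 0.756. Simulation gives 0.756, 0.784, 0.816 and 0.852 for q = 0, 0.2, 0.4 and 0.6.

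**If pre-enrollment relapses are not captured.** The event becomes the first relapse after enrollment, still timed from initiation. The observed value is then the average of e^(−λ·max(0, 1−a)) over enrolled patients. For λ = 0.25 and A = 2 it is 0.934 to 0.939 for q from 0.5 down to 0, about +16 points. Across the simulated scenarios the shift was about 6 to 26 points.

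**Check of the delayed-entry repair.** Entry was set at enrollment and restricted to patients relapse-free at entry. For λ = 0.25, A = 2 and q = 0.5, the estimate is 0.778 against a true 0.779 at one year, and 0.606 against 0.607 at two years. Over all scenarios run, the difference was at most about 0.006.

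**Clocks side by side.** For an experienced patient who relapsed between initiation and enrollment, that relapse ends time to first relapse. It falls outside the person-time that ARR divides by and before the baseline from which cNEDA is counted.

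**The case against.** The strongest objection is that the protocol does not discard pre-enrollment relapses. It says "For patients with previous exposure to Plegridy prior to enrollment, data will be collected from the time of first dose of Plegridy through enrollment", takes relapse history at baseline and can link the earlier studies. Entry does not require a patient to be relapse-free. This stands, and it rules out a reading a reader might otherwise adopt: classical left truncation, with experienced patients all event-free by construction and a 1-year proportion near 95%. That figure needs the planned capture to fail, which the protocol does not say it will. Failure is a risk, not a plan. Section 8.2.4.1 refers to Section 8.3.1 for details of this collection, but 8.3.1 covers only site and physician characteristics.

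The bias is also conditional. If stopping is unrelated to relapse and capture is complete, it is zero, and nothing in the documents shows how strongly relapse drives stopping. This stands too.

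A reader might further infer that a naive-versus-experienced contrast would be misread as a benefit of longer treatment. No such comparison is planned; the cohorts are kept apart and no formal hypothesis is tested. Nor does the point extend to time to sustained progression. That endpoint is measured from baseline EDSS, and no initiation origin is stated for it.

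Two objections stand only in part. Endpoints may legitimately use different clocks because they answer different questions, but a reader of the experienced cohort then needs to be told so. The estimator is open: Kaplan-Meier is named only for progression, and the SAP, not available here, may specify delayed entry. But the protocol itself fixes the origin without exception, and an SAP that follows it as written inherits the problem.

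**Conclusion.** The point holds in a limited form. The stated origin counts pre-enrollment time as ordinary time at risk in the Plegridy-experienced group, although entry required Plegridy still to be prescribed. With full capture, what remains is survivor selection through treatment persistence: roughly +2 to +10 points in the 1-year relapse-free proportion if 20–60% of relapsing patients stop, and none if stopping is unrelated to relapse. It is larger if earlier relapses are missed. These sizes rest on assumed hazards, prior exposure and stopping probabilities; the protocol also does not give the share of experienced patients among the 1100. The naive group is unaffected. The mismatch of clocks with ARR and cNEDA exists whatever the size of the bias. Severity is minor to moderate, since this is one descriptive secondary endpoint in one cohort.

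**What to change.** - **Plegridy-naive patients:** keep initiation as the origin.
- **Plegridy-experienced patients:** start the clock at enrollment and count only later relapses. This matches the cNEDA baseline and the ARR time base. It answers a different question: time to the next relapse among patients already established on treatment.
- **If time since initiation is wanted for experienced patients:** use delayed entry at enrollment, restricted to patients with no relapse between initiation and enrollment. This relies on complete pre-enrollment relapse data and on stopping before any relapse being unrelated to later relapse risk.
- **Pre-enrollment relapses:** report them descriptively, and correct the reference to Section 8.3.1 so that it points to where their collection is described.

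The cost is one definition in Section 8.6.5.4, carried into the SAP, using dates the protocol already plans to collect. The downside is that pre-enrollment relapses no longer contribute events to this endpoint. Under delayed entry, experienced patients who relapsed before enrollment also drop out of it.
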